Each participant will be asked whether he/she would be willing to donate a small amount of blood for the relation of genetic markers for mental health, substance abuse, and brain function. There is a separate consent form for this part of the study. DNA will be extracted from this blood sample and stored in a freezer at DHMC, labeled only with the subject's ID number, and the date of blood draw. There are several methods that may be used to genotype the study population. We will choose the most cost-effective, accurate and scientifically

appropriate methods at the time of processing. Options will include standard or custom single SNP and genome-wide arrays, as well as intermediate density sampling such as the custom 3300-SNP microarray designed by the PI and colleagues at Dartmouth. Genotyping will be carried out within Dartmouth and/or other qualified genotyping facilities, such as Illumina or Affymetrics, as appropriate depending on the assay conducted. If blood is sent to a facility such as Illumina or Affymetrics for testing, unused portions of the samples will be destroyed or returned to Dartmouth. The samples will be stored in de-identified form at Dartmouth until all the studies and assays associated with the research program have been completed. Analyses will be conducted at the single SNP level and at the level of complex gene-gene interactions and multivariate biological pathways in conjunction with the Computational Genetics Lab at Dartmouth.

5. Inclusion/Exclusion Criteria:

Please provide detailed description of inclusion and exclusion criteria. If a formal protocol for the study exists, page references to the protocol are acceptable.

Inclusion Criteria:

Groups 1-3 - Participants with SCZ-CUD

1. Ages 18 – 55 years old, inclusive
2. Diagnosis of schizophrenia or schizoaffective disorder as confirmed with the Structured Clinical Interview for the DSM (SCID)
3. Diagnosis of cannabis abuse or dependence as confirmed by the SCID
4. Use of cannabis within the month prior to screening based on the TLFB
5. Willing to remain abstinent for the 7 days before the baseline assessments and 14 days before the two scan days. Note: If the 14 day period of abstinence is too great a barrier for participants, the PI may decrease the amount to 7 days.
6. Psychiatrically stable as indicated by being treated as an outpatient for the past month as determined by a study physician's review

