Overall Approach to Protecting Study Participants: The PI and the DSMB will monitor safety throughout the study. We will obtain careful informed consent and insure that each participant fully understands the study procedures and the fact that for participants with SCZ-CUD both cannabis and dronabinol may cause a transient increase in symptoms and side effects. Confidentiality will be maintained with the standard procedures described below. A participant's clinical status will be monitored throughout the protocol and care will be coordinated with each person's clinical treatment team. Study participants may discontinue a study procedure at any time if they are uncomfortable or the study procedures appear to be causing exacerbation of illness.

Risk of potential exposure to COVID-19

Due to the pandemic beginning in 2020, there is a risk of potential exposure to COVID-19. For participant safety and safety of study staff we will follow all Dartmouth-Hitchcock procedures to reduce risk of infectious disease transmission. As of April 2021, we will use the following procedures during all study visits, and procedures will be adjusted as recommended by Dartmouth-Hitchcock.

- DH employees (potential participants and study staff) will complete any COVID-19 risk screening requirements per DHMC policy (currently on-line screening or in-person with door screeners) prior to entering the building.
- Non-DH employees will be screened at entrances staffed with door screeners.
- Whether they participate in on-line or in-person screening, the participant and all study staff must meet all DH COVID-19 screening requirements in order to be allowed into the medical center. If the participant/staff has symptoms or risk of exposure, research visits will not take place until the situation has resolved.

- Participants and all study staff will be required to wear a facial mask over their nose and mouth. If the participant does not have one, they will be provided with one. Participants will be required to wear the mask at all times with the exception of while they are in the MRI scanner. Study staff will also wear eye protection.
- Surfaces and equipment will be cleaned per medical center policy
- Study staff will practice frequent handwashing per DHMC guidelines.

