Risks from Cannabis and Dronabinol - Symptom Exacerbation: In this study, the most prominent activity associated with risk is the administration of cannabis and dronabinol, particularly to Groups 1, 2 and 3 who have a diagnosis of SCZ and a co-occurring CUD. Multiple strategies will be used to protect patients with SCZ-CUD who are given cannabis or dronabinol (or double-blinded cannabis and placebo) from relapse of psychosis. First, patients will be under treatment for their psychosis during the study, and must be stable with a low level of symptoms in order to participate. Second, all participants who will be exposed to cannabis or dronabinol during the study will be current active cannabis users who are used to the effect of cannabis. Third, with our pilot work, we have established a safe dose of dronabinol (two 7.5 mg capsules) and of cannabis for the cigarette for these patients, which did not produce untoward effects. We will use these doses in this study. All participants given cannabis or dronabinol (or double-blinded placebo cannabis and dronabinol) will be monitored closely in the laboratory until it is determined by the MD that they are able to be safely discharged. If symptoms develop and do not remit, patients will be offered inpatient treatment, as appropriate. Moreover, for participants given cannabis, dronabinol or placebo, we will attempt to contact them both the day after T2 and one week later to assess their status. If additional check-ins or clinical interventions are needed, it will be coordinated by the study team. In our pilot study with 15 patients in a similar protocol, none had problematic symptoms and no patients required additional medication or inpatient treatment. With the use of the strategies described here, study participation is unlikely to precipitate significant symptom exacerbations, but research staff, who have substantial clinical experience with this population, will be prepared to act immediately to treat patients and maintain safety if an exacerbation does occur.

Risks from Cannabis and Dronabinol - Other: Known effects of dronabinol and cannabis are listed below. These side effects occurred when people took dronabinol regularly. They are also known to occur when people smoke cannabis. We do not know how likely it is that these

side effects will occur if the medication is taken once as it will be in this study. Participants will be monitored frequently in the lab all day on the days they take these drugs.

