Common side effects: A "high" feeling (e.g. laughing easily, feeling happy, having a heightened awareness)

Occasional side effects (reported in 3-30% of people): Paranoia, confusion, nervousness, sleepiness, dizziness, stomach pain, nausea with or without vomiting, tachycardia, flushed face

Rare side effects (reported in less than 3% of people): Red eyes, diarrhea and/or incontinence, depression, nightmares, trouble speaking, visual problems, ringing ears, low blood pressure

Seizures have been reported in people taking dronabinol. Patients with a history of a seizure disorder will be excluded from this study.

Recruited patients with dual diagnosis and participants with CUD (without schizophrenia) will all be frequent cannabis users. Thus, we do not expect anything more than minimal effects from the modest dose of THC in the cannabis cigarettes or the two 7.5 mg dronabinol capsules. However, as with the potential of symptom exacerbation in the dual diagnosis patients (above), we will monitor all CUD patients until it is determined by an MD that they can be safely discharged and be prepared to act immediately to provide treatment and to maintain participant safety. Moreover, participants in Groups 1-3 and Groups 5-7 will have a baseline medical history and physical assessment to rule out medical contraindications to administration of dronabinol or cannabis. The assessment will include blood pressure, EKG, complete blood count and blood chemistry screen. All women in the study will have a pregnancy test as described in the section on assessments.

Risk Related to Confidentiality: This research involves monitoring and treatment of patients who use cannabis, an illegal substance. Participants may engage in other illegal activities. Maintaining confidentiality is an area of utmost importance for this population.

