Risks from Cannabis Withdrawal: Heavy cannabis users who discontinue use during the study may experience symptoms of cannabis withdrawal, involving nervousness, sleep disturbance, and appetite changes. Withdrawal from cannabis is not medically dangerous, and does not result in known long-term negative consequences. Since patients with schizophrenia tend to be light users of cannabis, we do not expect substantial cannabis withdrawal symptoms in our dual diagnosis participants. Some CUD (without SCZ) participants, if they are heavier users, may experience some withdrawal symptoms.

Participants will be educated about cannabis withdrawal with a fact sheet that includes a brief list of coping strategies. If participants experience cannabis withdrawal, research staff will cue the participant to use coping strategies and, if needed, will link the patient with clinical support from their treatment team (for patients with SCZ-CUD) or from clinical staff at DHMC (for participants with CUD alone).

Risks to Fetuses and Nursing Infants: Cannabis is known to be harmful to fetuses. Dronabinol is a pregnancy category C medication. The risks of brain fMRI for pregnant or nursing mothers to fetuses and to nursing babies are unknown. Thus, pregnant or nursing mothers will not be included in the study.

A urine pregnancy test, paid for by the study will be given to all women at the initial assessment, and on the morning of each scan day (i.e., thus before administration of cannabis, dronabinol or placebo and before scanning). If a participant is pregnant at baseline or becomes pregnant, she will be informed immediately, referred to her psychiatrist and/or her primary care physician, and discharged from the study. She will not undergo scanning nor be given cannabis or dronabinol.

Risks Related to Genetic Testing: The risks from genetic testing are mostly related to confidentiality and others (e.g. an insurer) learning a participant's results. To protect them from this type of risk, test results will be kept private. Information about participants will be coded with a number, not their name. Only the researchers in this study will be able to know the results of testing. The results of the genetic test will not be told to participants, treatment providers or others outside of the study. The results of the test will not be included in participants' medical records.

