- *people with a disabling psychiatric illness*
- *people who are economically disadvantaged persons*
- *people who are illiterate*

Refer to: Students, Employees Attachment D
Illiterate Subjects Attachment E

a) List vulnerable groups: *or check None*

We are studying people with schizophrenia, who are typically disabled by their psychiatric illness and are often economically disadvantaged. We do not anticipate recruiting Illiterate participants, but cannot rule it out. If this occurs, we will follow the CPHS guidance (see Attachment E). Some persons who are employees of Dartmouth, DHMC or our recruitment sites may wish to participate in this study.

b) Describe additional protections: *or check* N/A

We will utilize all of the strategies we typically use in our studies of individuals with serious mental illness. We will conduct a careful informed consent. People who are unable to provide informed consent due to a lack of clear understanding of the potential risks (or for other

reasons) will not be included in the study. We have a system of careful monitoring and backup treatments and supports to employ should a participant have difficulty, including a 24 hour availability of clinicians and psychiatrists who are experienced in the treatment of persons with co-occurring schizophrenia and cannabis use disorder. Because many participants do not have regular telephone service, thereby limiting their access to our emergency number, we will provide those participants who express the need for a telephone with a prepaid cellular phone (e.g. Tracfone) for use during the study. This telephone would also be used for reminder calls and in case the doctor and participant agree that a telephone check-in is warranted. To avoid exploiting persons who are economically disadvantaged, we are not making the stipend provided to participants unduly high. It is similar to what was offered in our previous study. In terms of students and employees who wish to participate in this study, we are not specifically recruiting these populations but also would not deny them access to the study. They would have the same careful protections to the confidentiality of their data as other participants and the consent forms clearly spell out the issues of who has access to study data.

19. Gender and Racial/Ethnic distribution:

NIH guidelines state that research involving human participation should include minorities and both genders.

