a) The reasons why the sponsor or funding agency is not accepting responsibility for research-related injury.

NIH does not cover the cost of injury or illness.

b) Summary of risks as related to potential costs that could be incurred as a result of research-related injury or illness.

It is possible that a participant could have a severe psychiatric reaction to the drugs used in the study or to the scanning or other study procedures. Should this occur, hospitalization could be required. However, we believe this is extremely unlikely given our pilot work establishing a safe dose of cannabis and dronabinol for this study and since all participants who get study drug will be cannabis users, some schizophrenia patients will be taking antipsychotic medication already, and all will be required to be psychiatrically stable as indicated by outpatient treatment for the past month. If a participant needs psychiatric hospitalization, it will be billed to their insurance.

c) Describe reasons for requesting that DHMC or Dartmouth College provide coverage for research-related injury or illness, which is not standard policy.

We are not requesting this.

29. Participant Remuneration:

Will participants be paid for their time, reimbursed for travel or meal expenses, or receive any sort of "gift" for participating in this study?

Yes No

If yes, please describe in detail:

Note: Participant remuneration is not considered a benefit of being in a research study. CPHS will consider the amount of payment in relation to the time needed and any inconvenience to participants. Payment, reimbursement, or gifts should not be in an amount that would be coercive to the participant population.

If study is to be done at the VA, specific questions need to be answered if a participant is being paid "in excess of reimbursement for travel." Please contact the CPHS office if you need more information.

Participants with schizophrenia will receive a \$25 gift card for attending the informational session to learn about the study.

All participants in Groups 1-4 (SCZ-CUD and SCZ only) will be paid:

- \$25 for completing the Screening Visit paid as a gift card on the day of the visit
- \$50 for the Neuropsych Baseline Visit paid as a check at the end of the study
- \$100 for T1 Scan day paid as a check at the end of the study

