In addition, when a study may involve subjects who lack capacity to give informed consent, the investigator will use the form provided below to inform the CPHS of the requested options to provide permission for an individual who lacks capacity to participate in the research study and respond to specific CPHS questions.

For all requests:

Even with the permission of a DPAHC, or court appointed legal guardian, the CPHS will not permit a subject who lacks capacity to give informed consent to participate in a research study that offers little chance of DIRECT BENEFIT to the research subject over what they could receive outside the research setting and involves a meaningful increase in the risk of harm or discomfort, regardless of the potential gain to future subjects or society in general.

Please complete a) and b):

- a) Does participating in this study offer the subject a chance of direct benefit over what they could receive outside the research setting?

We will allow individuals with legal guardians who meet eligibility criteria for Groups 1-3 - Participants with SCZ-CUD and Group 4 - Control participants with SCZ to participate in this study. Persons who have a legal guardian but do not have schizophrenia (Groups 5-8) would not qualify for this study.

For persons in the SCZ-CUD group, there is a direct benefit because there is really no place from which they could receive the contingency management program that is used to help people to abstain while in this study. For control participants with SCZ (but not CUD), there is no direct benefit.

b) *Is there an increase in the risk of harm or discomfort for the subject over what they would experience outside the research setting?*

No - The MRI, blood draws and other testing are routine non-invasive medical procedures that many people experience. Participants in the SCZ-CUD group may be exposed to THC through a capsule or by smoking it on a single instance, but persons meeting the criteria for these groups take this (through marijuana use) on their own on a regular basis.

When there is a meaningful chance of DIRECT BENEFIT to the research subject over what they could receive outside the research setting, the CPHS will make a judgment decision about who may consent to participation in the study. The options include: DPAHC, court appointed legal guardian, and a properly motivated next-of-kin.

Please indicate the option(s) requested to allow for consent if a subject is incompetent to provide consent:

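### The plan gives opposite rules on enrolling people who cannot consent, and Attachment G denies any added risk on a level of cannabis use that eligibility does not require

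*Combined protocol and SAP*

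**What the plan says.** **Capacity.** Section 18, item b, describes "People who are unable to provide informed consent due to a lack of clear understanding of the potential risks", or for other reasons, and says they will not be in the study. It makes no exception for guardians. Section 26 halts consent when capacity is in doubt and there is no guardian. It refuses recruitment when the treating psychiatrist finds that the person cannot consent and there is no guardian. Attachment G, item a, lets people with legal guardians enter Groups 1-3 and Group 4, but not Groups 5-8.

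**Level of use.** Section 14 (other risks of cannabis and dronabinol) states: "Recruited patients with dual diagnosis and participants with CUD (without schizophrenia) will all be frequent cannabis users". Attachment G, item b, states that "persons meeting the criteria for these groups take this (through marijuana use) on their own on a regular basis". The use criterion in Section 5, for Groups 1-3 and again for Groups 5-7, is: "Use of cannabis within the month prior to screening based on the TLFB". It stands beside a SCID diagnosis of abuse or dependence. On withdrawal, Section 14 says: "Since patients with schizophrenia tend to be light users of cannabis, we do not expect substantial cannabis withdrawal symptoms in our dual diagnosis participants".

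**Risk.** Attachment G, item b, asks whether the study adds risk of harm or discomfort over life outside it, and answers No. Section 14 says that "for participants with SCZ-CUD both cannabis and dronabinol may cause a transient increase in symptoms and side effects", and that "the most prominent activity associated with risk is the administration of cannabis and dronabinol", above all in Groups 1-3. Section 28, item b, says: "It is possible that a participant could have a severe psychiatric reaction to the drugs used in the study". It adds that admission to hospital might follow and that the team thinks this extremely unlikely.

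**The concern.** Two separate statements in the plan bear on the same decision: whether a patient with schizophrenia who cannot consent may be enrolled and, in Groups 1-3, randomised to receive THC.

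First, the enrolment rule has two opposite forms. A clinician who follows Section 18 turns away a person without capacity who has a guardian. A clinician who follows Section 26 and Attachment G may continue.

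Second, the review board's policy in Attachment G bars a person without capacity, even with a guardian's permission, when the chance of direct benefit is small and the added risk is meaningful. The sponsor's answer to the risk question is a flat No. For THC, that answer depends on a level of use that the criteria do not secure. It also does not fit the sponsor's own account of risk in Sections 14 and 28.

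**Working it through.** The plan states no figure on this point, so the check sets the texts side by side, with one small calculation.

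1. **Enrolment of a person who lacks capacity and has a guardian.**
   - Section 18: not included.
   - Section 26: the stopping rule needs both doubtful capacity and no guardian, so it is not triggered.
   - Attachment G, item a: may enter Groups 1-4.
   - Section 5 lists having a legal guardian as an exclusion for Groups 5-7 and Group 8, but not for Groups 1-3 or Group 4. The conflict therefore covers Groups 1-4.

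2. **Least use that meets the criteria.** Section 5 sets no frequency or quantity and does not say that the diagnosis must be current. One day of use in the month before screening is enough. Taking the month as 30 days (my assumption), Section 4 allows up to 10 weeks from screening to T1 before eligibility is repeated. It sets a T1-T2 target of 7 days, a minimum of 2 and no maximum. The longest gap from last use to dosing, for someone who abstains throughout, is:
   - at the target interval: 30 + 70 + 7 = 107 days;
   - at the minimum interval: 30 + 70 + 2 = 102 days;
   - with a longer T1-T2 interval: no upper limit.

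   Such a person is eligible but has not been shown to be a frequent or regular user. Section 15 describes the dosed groups in terms that do match the criteria: a CUD diagnosis with recent use.

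3. **The No in item b.** It has two grounds. One is that scanning, blood draws and testing are routine. Section 14 nevertheless lists scanner noise and confinement, and pain or bruising from the needle, and calls the long-term risk of two brain scans unknown. The question covers discomfort as well as harm. The other ground is regular use, which step 2 shows is not required. Against both stand the statements in Sections 14 and 28.

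4. **The pilot claim.** Section 15 says the pilot showed quite clearly that new or unusual effects are unlikely. Section 14 gives the result: none of 15 had problematic symptoms. The preliminary studies in Section 3 describe 15 subjects, compare dronabinol 5, 10 and 15 mg, and report imaging after drug in 6 given cannabis and 6 given dronabinol. The number of the 15 who received a study dose cannot be recovered from this.

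**The case against.** The best defence has five parts.

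**The guardian route looks deliberate.** The exclusion lists and Attachment G agree on it, Section 18 may be only the ordinary first-person consent rule, and having a guardian is not the same as lacking capacity. This stands as a reason to offer the sponsor a choice. It does not reconcile the texts, because Attachment G is the form for people who lack capacity and Section 18 allows no exception.

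**Item b is comparative.** Sections 14 and 28 state absolute risks. Section 15 says effects new to the participant are unlikely, and Section 14 calls everyone who is dosed a current active user accustomed to cannabis. A SCID diagnosis also suggests a pattern of use, and light use can be regular. With the stability criteria, physician checks and monitoring, this supports low risk. It does not support none.

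**The review board decides.** It sees Sections 14 and 28 in the same submission. A reader might infer that staff could dose a patient without capacity on the plan's authority alone, or that a corrected item b would bar Groups 1-3. The documents support neither. The public text stops before the option for who may consent is chosen. The bar needs little direct benefit as well as meaningful added risk, and item a claims a direct benefit for SCZ-CUD.

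**The benefit is real.** A reader might reduce contingency management to the estimated $450 of abstinence payments in Section 29. Section 4 also describes frequent testing, withdrawal education and withdrawal assessment, and Section 14 adds coping strategies and links to clinical support. The narrower reading fails.

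**Numbers for harm do not measure this defect.** A reader might take 0 of 15 as an exact upper 95% limit of 1 - 0.025^(1/15) = 21.8%, or about 11 of the 50 SCZ-CUD patients given active THC. The 15 cannot be shown to have had a study dose, and the 50 are everyone dosed in SCZ-CUD, not those without capacity. The 3-30% band for occasional effects in Section 14 comes from regular dosing, and the plan says single-dose likelihood is unknown.

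**Conclusion.** The concern holds in two parts. The plan contains opposite enrolment rules for people in Groups 1-4 who lack capacity and have a guardian. The flat No in Attachment G, item b, is not supported by the rest of the plan; low risk with safeguards is. For THC, that No rests on regular use, which the eligibility criteria do not require, and Section 14's statement that all are frequent users has the same fault.

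Group 4 should not be overlooked. It receives no drug, but item a concedes that it has no direct benefit, so the risk answer alone carries the board's test there.

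The size cannot be given as a count, because the documents do not say how many participants have guardians or lack capacity. Nothing here shows that harm is likely, and no endpoint, power figure or analysis changes. The plan should be corrected because the text governs who may be given THC without their own consent and what the board is told. The verdict assumes that the unseen remainder of Attachment G does not itself resolve the conflict with Section 18.

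**What to change.** 1. **One capacity rule.** Add to the exclusions for Groups 1-3 and for Group 4: *Lacks capacity to give informed consent, as assessed by the study physician or ARNP, whether or not the person has a legal guardian.* In Section 26, delete both conditions that make stopping depend on the absence of a guardian. In Attachment G, item a, limit Groups 1-4 to people with guardians who retain capacity. Groups 5-8 already exclude people with guardians.
2. **Item b for Groups 1-3.** Answer: *Yes, low and mitigated. THC may transiently increase symptoms; a severe reaction is possible but considered extremely unlikely.* List the scanner and cannula discomforts from Section 14.
3. **Level of use.** In Section 14 and Attachment G, item b, replace the frequent-use and regular-use claims with Section 15's description, a CUD diagnosis with recent use. In Section 14, drop the word that presents minimal effects as following from frequent use. No use threshold is needed.
4. **Pilot claim.** In Section 15, write: *None of 15 pilot patients had problematic symptoms; not all are shown to have received the study dose.* Give no confidence interval.

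The cost is two exclusion items and wording. There is no new visit, test or change in sample size, because Section 26 already has a physician or ARNP assess every candidate's capacity. Infrequent users stay eligible, as do people with guardians who retain capacity. The people lost are those who cannot consent, whom Section 18 already excludes. If the sponsor prefers the guardian route, it should delete the Section 18 sentence and obtain a board decision on the corrected item b.
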